9.3 Overdose

An overdose is defined as the accidental or intentional administration of any dose of a product that is considered both excessive and medically important. All occurrences of overdose must be reported as an SAE (see [Section 9.2](#)).

For this study, any dose of cabiralizumab and/or nivolumab greater than the assigned dose, and considered excessive and medically important by the Investigator will be considered an overdose.

9.4 Safety

Planned time points for all safety assessments are listed in the Schedule of Activities.

9.4.1 Physical Examinations

Refer to Schedule of Activities. Standard physical examination will be performed as determined by the Investigator, particularly to follow physical findings to resolution. Targeted physical exams should be conducted at any time to follow up on AE reports.

9.4.2 Vital signs

Refer to Schedule of Activities. Vital signs include respiratory, heart rate, blood pressure, and temperature in the resting position (sitting or supine). Measure prior to dose and after completion of each IV infusion at the following time points: 10 (± 5) minutes, 30 (± 10) minutes, and 60 (± 15) minutes, 168 hours (± 24 hours) [Cycle 1 only] post cabiralizumab administration; 10 (± 5) minutes post nivolumab administration. Pulse oximetry is performed at rest and after exertion prior to nivolumab dosing at each dosing visit only for the combination cohorts.

9.4.3 Electrocardiograms

Refer to Schedule of Activities. 12-lead ECG will be obtained at screening, pre dose and post dose of cabiralizumab (within one hour of completion of cabiralizumab) on C1D1 and C2D1, and end of treatment. If clinically indicated, additional ECGs may be obtained during the study. To minimize variability, it is important that patients be in a resting position for at least 5 minutes prior to each ECG evaluation.

9.4.4 Clinical Safety Laboratory Assessments

- Investigators must document their review of each laboratory safety report.
- A local laboratory will perform the analyses and will provide reference ranges for these tests.
- Results of clinical laboratory tests performed at Day 1 on each cycle must be available prior to dosing (unless obtaining assessment results are not possible due to local laboratory feasibility).

Hematology

Hemoglobin

Hematocrit

CBC including differential

Platelet count

RBC

Serum Chemistry	
Aspartate aminotransferase (AST)	Albumin
Alanine aminotransferase (ALT)	Sodium
Total bilirubin	Potassium
Direct bilirubin	Chloride
Alkaline phosphatase	Calcium
Lactate dehydrogenase (LDH)	Phosphorus
Creatinine	Creatine kinase
Blood Urea Nitrogen (BUN)	Tropoains
Glucose	Amylase
Cholinesterase	Lipase
	TSH
	FT3, FT4
	PT/INR
	PTT(aPTT)
Urinalysis	
Protein	
Glucose	
Blood	
Serology	
Serum for hepatitis C antibody, hepatitis B surface antigen, HBc antibody, and Interferon-Gamma Release Assays (e.g. Quantiferon test) (screening only)	
Other Analyses	
Pregnancy test (WOCBP only: screening, predose).	
Follicle stimulating hormone (FSH) (screening only for women only) if required	

If CK elevation is clinically significant, obtain troponins (cardiac), CK isoenzymes, aldolase, and ECG; repeat CK and these additional tests within 48 hours or other interval as clinically indicated, until resolved or stable. If either AST or ALT is elevated, obtain total serum bilirubin, alkaline phosphatase; repeat within 48 hours or other interval, as clinically indicated, until resolved or stable. Additional tests may be obtained at any time, if clinically indicated. If a patient is being followed for a tumor marker (e.g. CA-125, or others), a sample for the tumor marker should be obtained at screening and every other cycle, or if clinically indicated during the study.

9.4.5 *Optional Liver Biopsy*

Optional liver biopsy may be performed at the discretion of the Investigator with an agreement with the Sponsor in the presence of significant liver enzyme elevations. It is performed to understand whether or not such elevations are clinically/pathologically relevant.

9.4.6 *Imaging Safety Assessment*

Any incidental findings of potential clinical relevance that are not directly associated with the objectives of the protocol should be evaluated and handled by the Study Investigator as per standard medical/clinical judgment.

9.5 Pharmacokinetic and Anti-Drug Antibody (ADA)

Pharmacokinetics of cabiralizumab and nivolumab will be derived from serum concentration versus time data. The pharmacokinetic parameters of cabiralizumab to be assessed, following the intensive PK collection after first dose, are shown in below.

AI_Ctrough	Ctrough Accumulation Index; ratio of Ctrough at steady-state (i.e. Cycle 8) to Ctrough after the first dose
AUC(0-T)	Area under the serum concentration-time curve from time zero to time of last quantifiable concentration after the first dose
AUC(TAU)	Area under the serum concentration-time curve in one dosing interval
Cmax	Maximum observed serum concentration
Ctrough	Trough observed serum concentration (predose at each cycle)
T-HALFeff_Ctrough	Effective elimination half-life that explains the degree of Ctrough accumulation observed
Tmax	Time of maximum observed serum concentration

Individual participant pharmacokinetic parameter values will be derived by non-compartmental methods by a validated pharmacokinetic analysis program. Actual times will be used for the analyses.

Table 9.5-1 and [Table 9.5-2](#) are listed the sampling schedule for Cohort M1/M2 and C1/C2 to be the assessment of pharmacokinetics and immunogenicity respectively. Treatment assignments will be released to the bioanalytical laboratory in order to minimize unnecessary analysis of samples.

Additional samples for immunogenicity assessments, referred to as “ADA Event Driven” samples may be justified in cases of Grade 3/4 infusion or hypersensitivity reactions. The immunogenicity (and corresponding drug exposure) data from these samples will be reported as part of a subject’s overall immunogenicity assessment. Uniquely identified specimen collection kits and instructions for collection of “ADA Event Driven” samples will be provided by the central laboratory vendor

Table 9.5-1: Pharmacokinetic Sampling Schedule for Cohort M1 and M2

Study Cycle (Study Day)	Event	Time Hour: Min	Sampling for cabiralizumab	Sampling for ADA (cabiralizumab)
Cycle 1 (Day 1)	Prior to infusion	00:00	X	X
	EOI ^a	00:30	X	
	4 hr post-start of infusion	04:00	X	
Cycle 1 (Day 2)	24 hr post-start of infusion	24:00	X	
Cycle 1 (Day 4)	72 hr post-start of infusion	72:00	X	

Table 9.5-1: Pharmacokinetic Sampling Schedule for Cohort M1 and M2

Study Cycle (Study Day)	Event	Time Hour: Min	Sampling for cabiralizumab	Sampling for ADA (cabiralizumab)
Cycle 1 (Day 8)	168 hr post-start of infusion	168:00	X	
Cycle 2 – 3 (Day 1)	Prior to infusion	00:00	X	X
Cycle 4 (Day 1)	Prior to infusion	00:00	X	
Cycle 5 (Day 1)	Prior to infusion	00:00	X	X
Cycle 6 – 8 (Day 1)	Prior to infusion	00:00	X	
Cycle 9, 13, 21 (Day 1)	Prior to infusion	00:00	X	X
End of Treatment	Post treatment		X	X
Follow-up	-		X	X

^a EOI=End of Infusion, This sample should be taken immediately prior to stopping the infusion (preferably within 2 minutes prior to the end of infusion). If the end of infusion is delayed to beyond the nominal infusion duration, the collection of this sample should also be delayed accordingly.

Table 9.5-2: Pharmacokinetic Sampling Schedule for Cohort C1 and C2

Study Cycle (Study Day)	Event (Relative to cabiralizumab)	Time (Relative to start of cabiralizumab infusion) Hour: Min	Sampling for cabiralizumab	Sampling for Nivolumab	Sampling for ADA (cabiralizumab and Nivolumab)
Cycle 1 (Day 1)	Prior to infusion	00:00	X	X	X
	EOI ^a	01:30	X	X	
	4 hr post-start of infusion	04:00	X		
Cycle 1 (Day 2)	24 hr post-start of infusion	24:00	X		
Cycle 1 (Day 4)	72 hr post-start of infusion	72:00	X		
Cycle 1 (Day 8)	168 hr post-start of infusion	168:00	X		

Table 9.5-2: Pharmacokinetic Sampling Schedule for Cohort C1 and C2

Study Cycle (Study Day)	Event (Relative to cabiralizumab)	Time (Relative to start of cabiralizumab infusion) Hour: Min	Sampling for cabiralizumab	Sampling for Nivolumab	Sampling for ADA (cabiralizumab and Nivolumab)
Cycle 2 – 3 (Day 1)	Prior to infusion	00:00	X	X	X
Cycle 4 (Day 1)	Prior to infusion	00:00	X		
Cycle 5 (Day 1)	Prior to infusion	00:00	X	X	X
Cycle 6 – 8 (Day 1)	Prior to infusion	00:00	X		
Cycle 9, 13, 21 (Day 1)	Prior to infusion	00:00	X	X	X
End of Treatment	Post treatment		X	X	X
Follow-up	-		X	X	X

^a EOI=End of Infusion, This sample should be taken within 15 min after end of infusion for both cabiralizumab and nivolumab.

PK samples will be analyzed for cabiralizumab and nivolumab by validated immunoassays. Immunogenicity samples will be analyzed for anti-cabiralizumab and anti-nivolumab antibodies by validated immunoassays.

Serum samples may be used for potential exploratory bioanalysis (e.g., analysis of drug-ADA immune complexes); exploratory results will not be reported. Serum samples designated for immunogenicity, PK or biomarker assessments from the same collection time point may be used interchangeably, if required (eg, insufficient volume for complete assessment or to follow up on suspected immunogenicity related AE). In addition, serum samples will be archived, if the need arises and to the extent possible.

Detailed instructions for the pharmacokinetic blood collection, labeling, processing, storage, and shipping will be provided to the site in the procedure manual.

[REDACTED]

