7.5.1 Dosing of Cabiralizumab and Nivolumab

For patients in the monotherapy cohorts, cabiralizumab infusion will be administered as a 30-minute IV infusion on Day 1 of each 14-day treatment cycle. For the combination therapy, nivolumab should always be administered first as a 30-minute IV infusion followed by a 30-minute infusion of cabiralizumab. The time in between infusions is expected to be approximately 30 minutes but may be more or less depending on the situation. Cabiralizumab ± Nivolumab will be administered every 2 weeks in 14-day (\pm 2 days). Subjects may be dosed no less than 12 days from the previous dose.

Dosing calculations should be based on the body weight assessed at Cycle 1 Day 1 prior to the first dose of study drug administration. If the subject's weight on the day of dosing differs by $> 10\%$ from the weight used to calculate the prior dose, the dose must be recalculated. All doses should be rounded to the nearest milligram.

The calculated dose for Cabiralizumab may be mixed in 5% Dextrose Injection, USP or 0.9% Sodium Chloride Injection, USP to nominal concentrations of 1.0 mg/mL to 10 mg/mL which can be infused over a period of 30 minutes through an intravenous line containing a sterile 0.22 micron in-line filter. Further guidance and information for the preparation of the study medication is provided in the pharmacy manual.

The calculated dose for Nivolumab may be mixed in 5% Dextrose Injection, USP or 0.9% Sodium Chloride Injection, USP to nominal concentrations of 1 mg/mL – 10 mg/mL which can be infused over a period of 30 minutes through an intravenous line containing a sterile, non-pyrogenic, low-protein binding in-line filter. Further guidance and information for the preparation of the study medication is provided in the pharmacy manual.

[figure not shown]
Doses of study drugs may be interrupted, delayed, or discontinued depending on how the patient tolerates the treatment.

[figure not shown]
[figure not shown]
[figure not shown]
7.5.2 *Retained Samples for Bioavailability / Bioequivalence*

Not Applicable.

7.6 *Treatment Compliance*

Study treatment compliance will be periodically monitored by drug accountability. Drug accountability should be reviewed by the site study staff at each visit to confirm treatment compliance. Sites should discuss discrepancies with the participant at each on-treatment study visit.

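### Cabiralizumab's end-of-infusion sample is drawn just before infusion stop in M1/M2 but up to 15 minutes after it in C1/C2, a small, avoidable sampling difference in Cmax and Tmax

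*Protocol*

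**What the plan says.** Protocol Section 9.5 sets two sampling schedules for cabiralizumab.

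- Table 9.5-1 (M1/M2) lists EOI at 00:30. Its footnote a says "This sample should be taken immediately prior to stopping the infusion (preferably within 2 minutes prior to the end of infusion", and moves the sample later if the infusion overruns.
- Table 9.5-2 (C1/C2) lists EOI at 01:30, in a column headed "Time (Relative to start of cabiralizumab infusion) Hour: Min". Its footnote a says "This sample should be taken within 15 min after end of infusion for both cabiralizumab and nivolumab".

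In both tables the next sample is "4 hr post-start of infusion".

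Protocol Section 7.5.1 gives the infusion lengths. For monotherapy, "cabiralizumab infusion will be administered as a 30-minute IV infusion on Day 1 of each 14-day treatment cycle". For the combination, "nivolumab should always be administered first as a 30-minute IV infusion followed by a 30-minute infusion of cabiralizumab", and "The time in between infusions is expected to be approximately 30 minutes".

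Cmax has one definition for every cohort: "Maximum observed serum concentration". Section 9.5 says that parameters are derived from actual times. Protocol Section 10.3.3 and SAP Section 7.7.2 summarise Cmax by geometric mean and coefficient of variation, and Tmax by median and range; the SAP does this by cohort. SAP Section 7.7.1 summarises concentrations by cohort and nominal collection time, and puts the cohorts' mean profiles on one plot.

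**The concern.** The two footnotes place the same sample on opposite sides of infusion stop. In M1/M2 it is drawn while drug is still running in, so part of the dose has not yet been given. In C1/C2 it is drawn once the dose is complete, possibly after some decline.

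Describing cabiralizumab PK alone and in combination is a secondary objective, and M2, C1 and C2 receive the same 4 mg/kg. A reader will naturally set M2 beside C1 and C2. Only two samples lie near the peak (EOI and 4 hours), so a difference in the EOI rule can show up in Cmax and Tmax with no interaction between the drugs. Using actual times places the sample correctly on the time axis, but it cannot restore a concentration that was never sampled.

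The C1/C2 row has a second problem: its nominal time does not agree with its own column header or footnote.

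**Working it through.** **1. Nominal times.** In M1/M2 a 30-minute infusion ends at 00:30, which reproduces Table 9.5-1. In C1/C2, counted from the start of cabiralizumab as the header says, a 30-minute infusion also ends at 00:30. The table says 01:30. That figure is reproduced only on a clock started at nivolumab: 30 (nivolumab) + 30 (gap) + 30 (cabiralizumab) = 90 minutes. Read literally, 01:30 is 90 - 30 = 60 minutes after infusion stop, outside the footnote's 15-minute window.

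**2. EOI concentration.** Inputs from the documents are infusion length T = 30 min, an M1/M2 draw at 28 to 30 min (the preferred window), a C1/C2 draw at 30 to 45 min, and the shared sample at 240 min. The model is an assumption: one compartment and a constant infusion rate. With k = ln 2 / half-life:

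- during infusion, C(t) is proportional to (1 - exp(-kt)) / (kT);
- afterwards, C(t) = C(T) × exp(-k(t - T)).

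When decline is slow, the 28-minute value is close to the fraction of dose infused, 28/30 = 0.933, so it is 6.7% low.

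The documents give no early half-life for cabiralizumab, so a range of 2 hours to 30 days is assumed. The upper end matches the statement in Protocol Section 9.2.5 that equates 5 half-lives with 5 months, without naming the drug.

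**3. Cmax.** Take Cmax as the larger of the EOI and 4-hour samples. Concentrations below are relative to the level at infusion stop. The ratios are combination over monotherapy.

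| Assumed half-life | 28 min | 45 min | 4 h | Lowest ratio (45 vs 30 min) | Highest ratio (30 vs 28 min) |
|---|---|---|---|---|---|
| 2 h | 0.939 | 0.917 | 0.297 | 0.917 | 1.065 |
| 12 h | 0.934 | 0.986 | 0.817 | 0.986 | 1.070 |
| 24 h | 0.934 | 0.993 | 0.904 | 0.993 | 1.071 |
| 48 h | 0.934 | 0.996 | 0.951 | 0.996 | 1.052 |
| 7 days | 0.933 | 0.999 | 0.986 | 0.999 | 1.015 |
| 30 days | 0.933 | 1.000 | 0.997 | 1.000 | 1.003 |

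**4. When the 4-hour sample takes over.** It is drawn 3.5 h after infusion stop. It exceeds an EOI sample at fraction f of the peak when exp(-3.5k) > f, that is, when the half-life exceeds 3.5 × ln 2 / (-ln f).

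- For f = 28/30 this is about 35 h.
- For f = 25/30 (a draw 5 minutes early) it is about 13 h.

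Above these values the 4-hour sample supplies the M1/M2 Cmax and limits the loss. At 7 days the loss cannot exceed 1 - 0.986, about 1.4% of the peak (a ratio of 1.015), however early the EOI draw was.

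**5. Tmax.** The M1/M2 EOI sample gives a Tmax of 28/60 = 0.47 h to 0.5 h, against 0.5 to 0.75 h in C1/C2. Where the 4-hour sample takes over, the M1/M2 Tmax becomes about 4 h.

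**6. Scale of random error.** With 6 versus 6 subjects and an assumed between-subject CV of 20% to 40%, the 90% confidence factor for a ratio of geometric means is exp(t(0.95, 10) × s × √(1/6 + 1/6)), with s = √ln(1 + CV²). This gives a multiply-or-divide factor of 1.23 to 1.50.

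**The case against.** The strongest reply is that nothing planned depends on this. The objective is to characterise PK. Neither document plans a test, ratio or interaction claim between M2 and C1/C2, and random error in cohorts of about 6 is far larger than the shift. That stands, and it is why the point is minor.

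A reader might infer that Cmax is a different quantity in the two settings. The documents do not support this: there is one definition for all cohorts, it covers all samples, and both schedules contain the 4-hour draw. Only the sampling basis differs.

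A reader might also carry the EOI deficit straight into Cmax, for example 5/30 = 16.7% for a draw 5 minutes early. That deficit belongs to the EOI sample. It reaches Cmax in full only if the early half-life is below about 13 h, and the footnote's main instruction is to sample immediately before stopping, so a 5-minute lead is not what it asks for.

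Finally, one EOI row in Table 9.5-2 serves two drugs, and a procedure manual not available here holds detailed collection instructions. Either could explain a draw after the infusion in C1/C2. Neither explains, in the documents at hand, why M1/M2 needs the opposite rule.

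**Conclusion.** The point holds as a minor inconsistency. The sampling rules differ without a stated reason, and the M1/M2 EOI concentration can be up to about 7% below the end-of-infusion level when drawn at 28 of 30 minutes. The induced shift in the combination/monotherapy Cmax ratio runs from about -8% (half-life 2 h, C1/C2 drawn at 45 minutes) to about +7% (M1/M2 drawn at 28 minutes, half-life up to about 35 h). It is tempting to call this a consistent bias in one direction, but the sign depends on the early half-life and on when within each window the sample is drawn, and the range includes no shift. At a half-life of 7 days or more it is about 1.5% or less.

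These figures rest on a one-compartment model, a constant infusion rate, the preferred 2-minute window being kept, and assumed half-lives. The conflict over the 01:30 entry needs none of these assumptions. It matters because concentrations are summarised by nominal time: taken at face value, EOI would appear at 0.5 h for M1/M2 and 1.5 h for C1/C2 on the shared plot.

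**What to change.** 1. Use one EOI rule for cabiralizumab in Tables 9.5-1 and 9.5-2, with the same window relative to the actual stop of the cabiralizumab infusion. If the difference is intended, state the reason.
2. Reconcile the 01:30 EOI entry in Table 9.5-2 with its column header and footnote a, so that the SAP's nominal-time summaries use one clock in all cohorts.
3. For samples already drawn, flag in the PK listing each EOI sample taken before infusion stop.
4. Add a sentence on the sampling difference wherever Cmax or Tmax for M2 and C1/C2 are shown together.

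The cost is one footnote, one table entry or header, one listing flag and one sentence in the report. No extra sample is needed, and no dose or infusion time changes.

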After tolerability of a dose of 4 mg/kg cabiralizumab monotherapy has been confirmed in the DLT evaluation period of the study, combination cohorts for both subjects with solid tumor and subjects with hematologic malignancies will open in parallel. 6 subjects per each cohort will be enrolled. The start of combination cohorts needs to be agreed by the Efficacy and Safety Evaluation Committee. Subjects will undergo screening evaluations to determine eligibility within 28 days prior to the first doses of cabiralizumab and nivolumab on Day 1 of Cycle 1. Cabiralizumab at a dose of 4 mg/kg and nivolumab at a dose of 3 mg/kg will be administered every 2 weeks.

Sponsor has the option to expand the combination cohorts in order to obtain additional data or to investigate alternative dose levels to those defined in the protocol. Upon completion of 28 days follow-up from the first dose on initial 6 subjects on each combination cohort and after agreed by the Efficacy and Safety Evaluation Committee, up to 24 patients (12 patients with advanced solid tumor and 12 patients with hematologic malignancies) may be enrolled in combination cohorts to fully characterize safety, PK, and PD.

5.1.3 *Data Monitoring Committee and Other External Committees*

[figure not shown]
Efficacy and Safety Review Committee will be established in this study.

5.2 *Number of Participants*

Between 6 and 12 subjects are expected to be treated during dose escalation, assuming 2 mg/kg and 4 mg/kg cabiralizumab monotherapy are explored. On the combination cohorts, 6 subjects each cohort are expected to be treated with 4 mg/kg cabiralizumab in combination with 3 mg/kg nivolumab following the dose escalation part of monotherapy. In addition, Sponsor has the option to expand combination cohorts (up to 12 subjects in total per each combination cohort) at the dose previously established to be safe in order to obtain additional data or to investigate alternative dose levels to those defined in the protocol.

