Cabiralizumab and nivolumab may induce infusion or hypersensitivity reactions. If such reactions were to occur, it may manifest with fever, chills, rigors, headache, rash, pruritus, arthralgia, hypo- or hypertension, bronchospasm, or other symptoms.

Infusion reactions should be graded according to CTCAE v4 guidelines. Any Grade 3 or Grade 4 infusion reaction should be reported within 24 hours to the Sponsor's Medical Monitor or designee, and reported as an SAE if it meets the criteria.

The nivolumab 30-minute infusion will be administered first, with a 30-minute rest, followed by the cabiralizumab 30-minute infusion. It may be unclear if an infusion reaction is due to cabiralizumab, nivolumab, or to both study drugs. Therefore, one set of treatment recommendations (based on the most conservative treatments for infusion reactions due to either study drug) is provided below and may be modified based on clinical judgment, local treatment standards and guidelines, and/or specific symptoms, as appropriate:

For Grade 1 symptoms: Mild reaction (e.g., localized cutaneous reactions including mild pruritus, flushing, rash), requires infusion rate to be decreased; intervention may be indicated.

- Decrease the rate of the study drug infusion until recovery from symptoms.
- Remain at bedside and monitor the patient's vital signs until resolution of symptoms. Diphenhydramine 50 mg may be administered at the discretion of the treating physician.
- When symptoms resolve, restart the infusion at the original infusion rate.
- If a patient has an infusion reaction with nivolumab, cabiralizumab can be given (without prophylactic medications) if the infusion reaction resolves within 3 hours. For scheduling purposes, cabiralizumab infusion may be given the next day. Prophylactic pre-infusion medications should be given prior to all subsequent nivolumab infusions.
- If a patient has an infusion reaction with cabiralizumab, prophylactic pre-infusion medications should be given prior to all subsequent cabiralizumab and nivolumab infusions.
- The following prophylactic pre-infusion medications are recommended prior to future infusions of cabiralizumab and nivolumab: diphenhydramine 50 mg (or equivalent) and/or

paracetamol (acetaminophen) 325 to 1000 mg at least 30 minutes before additional study drug administrations.

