Section 9.4.4: Clinical Safety Laboratory Assessments	Delete skeletal from troponin obtained if CK elevation is clinically significant.	
Appendix 6.7.8	Modified in accordance with the changes in FPA008-003 protocol	
All	Minor formatting and typographical corrections	

Overall Rationale for the Revised Protocol 02, 06-Jul-2017

The main purpose of this revised protocol is to clarify and correct the following points in order to reduce ambiguity regarding study procedures:

- Clarify the allowance for physical measurements and laboratory tests on treatment phase
- Correct and clarify time and event for pharmacokinetic sampling schedule to be collected relative to start of cabiralizumab infusion

In addition, administrative changes are incorporated in the revised protocol.

The revised protocol applies to all participants.

SUMMARY OF KEY CHANGES FOR REVISED PROTOCOL 02	
Section Number & Title	Description of Change
Section2: SCHEDULE OF ACTIVITIES Table 2-1	1) Laboratory Tests was modified to include Troponin. 2) Documentation of extramedullary soft tissue plasmacytomas was modified to add notes to table.
Section2: SCHEDULE OF ACTIVITIES Table 2-2	5) Physical Measurements, pregnancy test and Laboratory Tests were modified to include within 72 hours prior in notes and add footnote. 6) Vital signs was modified to add notes to table. 7) EOT was removed from exploratory biomarker assessment
Section 6.1: Inclusion Criteria	1)-b)Consent for tumor biopsy samples in subjects with solid tumor was modified

SUMMARY OF KEY CHANGES FOR REVISED PROTOCOL 02	
Section Number & Title	Description of Change
Section 6.2: Exclusion Criteria	Exclusion Criteria was modified to include 1)-p) and q).
Section 7.2: Method of Treatment Assignment	Method of Treatment Assignment was modified to update participant numbers assignment.
Section 9.1.1.1:Imagining Assessment	11) The first sentence in the first paragraph was modified to include the mention of the end tumor assessment. 12) The last sentence in the last paragraph was added to include the mention of Treatment beyond Disease Progression.
Section 9.1.2.1: Laboratory Assessments	1) “Baseline” was modified in wording to “screening” 15) Serum free light chain and Urine parts were modified to include “starting from C3D1 to every 2 cycles”
Section 9.1.2.2: Skeletal Survey	The first sentence in the first paragraph was modified to include “during 28 days prior to initiation of study drugs” in

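### Table 9.5-2 times the Cycle 1 Day 1 end-of-infusion sample at 01:30 on a clock where the cabiralizumab infusion ends at 00:30

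*Protocol*

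**What the plan says.** Protocol Section 9.5 has one PK sampling table for monotherapy (Table 9.5-1) and one for the combination cohorts (Table 9.5-2). The event column of Table 9.5-2 is stated relative to cabiralizumab, and its time column is headed "Time (Relative to start of cabiralizumab infusion) Hour: Min". Appendix 12 names the same clock in its rationale for Revised Protocol 02: "Correct and clarify time and event for pharmacokinetic sampling schedule to be collected relative to start of cabiralizumab infusion". It is cited here only as a sign of which clock was meant; the current header settles the matter.

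On Cycle 1 Day 1, Table 9.5-2 gives a pre-infusion sample at 00:00, one EOI row at 01:30 ticked for both drugs, and a 4-hour sample at 04:00 for cabiralizumab. Footnote a to the EOI row reads: "This sample should be taken within 15 min after end of infusion for both cabiralizumab and nivolumab".

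Section 7.4.5 gives the infusion sequence: "The nivolumab 30-minute infusion will be administered first, with a 30-minute rest, followed by the cabiralizumab 30-minute infusion". Section 7.5.1 gives the same order and durations, and says the time between infusions is "expected to be approximately 30 minutes but may be more or less depending on the situation". In Table 9.5-1, the EOI of the same 30-minute cabiralizumab infusion is at 00:30.

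On analysis times, Section 9.5 says of the PK parameters: "Actual times will be used for the analyses". SAP 7.7.1 summarises concentrations of both drugs by cohort and nominal collection time. SAP 4.3.1 summarises nivolumab trough and EOI concentrations. SAP 7.7.2 summarises cabiralizumab Cmax and Tmax.

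**The concern.** The EOI cell disagrees with its own column header, with its own footnote and with the stated infusion duration. A site following the cell and a site following the footnote would draw the cabiralizumab sample 45 to 60 minutes apart.

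The EOI sample is the only one scheduled between the pre-dose draw and 4 hours. If it is taken an hour late, the concentration at the end of the infusion is not observed. Cabiralizumab PK alone and in combination is a secondary objective, and Cmax is one of its summarised parameters.

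There is also a display effect. SAP 7.7.1 puts mean profiles by cohort on the same plot. If nominal time is the printed value, the EOI point is at 00:30 in M1 and M2 but at 01:30 in C1 and C2.

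A second, softer question is what the single EOI row means for nivolumab, whose infusion has ended well before cabiralizumab finishes.

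**Working it through.** **Inputs.** Nivolumab infusion 30 min, given first; cabiralizumab infusion 30 min (Sections 7.4.5 and 7.5.1). The gap between them, g, is 30 min as planned but may vary. The footnote a window is 0 to 15 min after the end of infusion. The printed EOI time is 01:30 = 90 min.

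**Reproducing 01:30.** Counting from nivolumab start, cabiralizumab ends at 30 + g + 30 = 60 + g. With g = 30 this is 90 min = 01:30. So the figure can be reproduced, but only from nivolumab start and only with the planned gap. For assumed gaps of 0, 15, 45 and 60 min it would be 01:00, 01:15, 01:45 and 02:00.

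**Both clocks against the printed rows (g = 30).**

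| Event | Cabiralizumab-start clock (the header) | Nivolumab-start clock | Printed |
|---|---|---|---|
| Nivolumab ends | -g = -00:30 | 00:30 | no separate row |
| Cabiralizumab starts | 00:00 | 30 + g = 01:00 | 00:00 (pre-infusion row) |
| Cabiralizumab ends | 00:30 for any g | 60 + g = 01:30 | 01:30 |
| 4 h after cabiralizumab start | 04:00 | 60 + 240 = 300 min = 05:00 | 04:00 |

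No single clock fits both the EOI row and the 4-hour row. On the nivolumab clock the printed 04:00 would be 240 - 60 = 180 min after cabiralizumab start, not 240. The 4, 24, 72 and 168 h rows all agree with the header, so the EOI cell is the one out of line.

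**Size of the discrepancy on the header's clock.**
- After the end of cabiralizumab: 90 - 30 = 60 min.
- After the cabiralizumab window closes (30 + 15 = 45): 90 - 45 = 45 min.
- After the end of nivolumab with the planned gap: 90 - (-30) = 120 min.

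**One row for two drugs.** The infusions end 30 - (-g) = 30 + g min apart: 60 as planned, and at least 30 for any g of 0 or more. The windows are [-g, -g + 15] for nivolumab and [30, 45] for cabiralizumab. The time between them is 30 - (15 - g) = 15 + g min: 45 as planned, at least 15. No one draw can lie within 15 min of both ends. A single draw at the true end of cabiralizumab would be about 60 min after nivolumab ended.

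**The case against.** The strongest defence is that footnote a gives an event-based rule that does not depend on the clock cell, and that actual times feed the PK parameters. Sites may also be working from other text: "Detailed instructions for the pharmacokinetic blood collection, labeling, processing, storage, and shipping will be provided to the site in the procedure manual". That manual is not available, so nobody can say from these documents that any sample was drawn at 01:30. This stands as a limit on the impact. It does not make the cell right: if the footnote governs, the printed time contradicts it. Actual times correct a mislabelled sample, but they do not recover a concentration that was never drawn.

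A reader might infer that ticking one row for two drugs is itself an error. The documents do not support that. The footnote speaks of the sample in the singular and can be read as one draw after both infusions have finished. On that reading a single row is coherent and the separate windows do not matter. What remains is an ambiguity with a consequence: under one draw, the nivolumab value is not an EOI concentration in the sense that SAP 4.3.1 uses.

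A reader might also infer that pre-dose nivolumab PK and ADA samples are mistimed, because the pre-infusion rows refer to cabiralizumab. That too goes further than the text. Trough is defined as pre-dose (for cabiralizumab, with the same term used for nivolumab in the SAP), and baseline ADA is already tied to the start of treatment in Protocol Section 10.3.4 and SAP 6.1. This is missing detail, not an error.

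Finally, the comparison with Table 9.5-1 is not exactly like for like. Its EOI sample is taken just before the infusion stops, whereas the combination sample is taken up to 15 min after. That small difference does not explain a 60-minute one.

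**Conclusion.** The time in the cell is wrong as written. The conclusion needs only the table's header and the 30-minute cabiralizumab infusion, and it holds for any gap between infusions.

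The effect on cabiralizumab is conditional. If a site drew at 01:30, observed Cmax and Tmax could change. The available text gives no concentrations from the first hours after infusion, so the size of that change is not estimated here. If sites followed the footnote, what remains is a label that may shift the EOI point by 60 minutes in the nominal-time summaries. That shift arises only if nominal time means the printed value rather than the labelled event.

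The nivolumab point is a request for clarification. It bears on a descriptive summary listed under the SAP's other endpoints. The primary safety endpoint is not touched. The correction should be made, but it does not threaten the trial's main conclusions.

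**What to change.** 1. Keep the cabiralizumab-start clock in Table 9.5-2, change the cabiralizumab EOI time to 00:30, and say that footnote a's window governs.
2. State in footnote a which of two schemes applies to nivolumab:
   - it has its own draw at the end of its infusion, on its own row at about -00:30 with the planned rest and tied to the actual end of infusion; or
   - it shares the cabiralizumab EOI draw, in which case the nivolumab value should not be labelled or summarised as end of infusion in SAP 4.3.1.
3. Optionally, clarify that pre-dose nivolumab PK and ADA samples precede that day's nivolumab. With the planned rest nivolumab starts at -01:00, so the 00:00 label on those rows should then read pre-dose.

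The cost is a correction to one table and its footnote, with matching procedure-manual text. The separate-draw option adds one Cycle 1 Day 1 draw per combination subject if it is not already taken. That is 2 x 6 = 12 draws at the planned size and 2 x 12 = 24 at the maximum in Section 5.1.2 ("up to 24 patients (12 patients with advanced solid tumor and 12 patients with hematologic malignancies) may be enrolled in combination cohorts"). The shared-draw option adds none.
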